9. RESEARCH METHODS

9.1. Study Design

- **Retrospective analysis** of patients with SpA that received etanercept from Baghdad Teaching Hospital (Rheumatology Center) from May 2012 through August 2019.
- **Primary objective:** 1 and 7 years adherence of SpA patients on Enbrel.
- **Secondary objective:** The difference in efficacy between the adherent group of patients (who continued Enbrel treatment) and the nonadherent group.

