9.2. Setting

Patients and Methods

Data was collected from the Baghdad Teaching Hospital rheumatology registry. It captured all patients who have been treated with biologic therapies managed in the rheumatology department. The decision to initiate and maintain the treatment was guided by the American College of Rheumatology (ACR) recommendations.

Study population

Patients included in the study met the American College of Rheumatology/European League Against Rheumatism (EULAR) 2019 criteria for SpA⁶, with at least 1 year of follow-up after starting their first biologic therapy. Exclusion criteria: patients previously or currently treated with other biological treatments.

Hypothesis

There was a small percentage of patients who adhered to Enbrel over 7 years, and there was no difference between the adherent and the nonadherent group in efficacy.

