9.3. Data Sources

Patients were identified from the rheumatology patient registry with a SpA diagnosis and information was obtained on patient demographics (age, gender), education-level (years), present smoking status, disease duration (years), current MTX and steroid therapy (yes/no), baseline BASDAI, and BASFI and last assessment of baseline BASDAI and BASFI.

Primary Outcomes: was the percentage of patients that have 7 year adherence on Enbrel.

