9.6. Data Analysis

All covariates will be summarized to get information about frequency distribution and mean, median or standard deviation. Numbers and percentages will be provided for dichotomous and polychotomous variables when performing descriptive analysis of categorical data. Means, medians, standard deviations, and interquartile range as appropriate will be provided for continuous variables when performing descriptive analysis of continuous data. Patients will be assessed for first-year adherence (first-year adherence is defined as patients having at least 7 consecutive visits in one year of Enbrel treatment), then the 7-year adherence will be assessed and the percentage of patients that achieve 7-year adherence will be calculated. The difference between adherent and nonadherent groups in baseline visit and last visit BASDAI and BASFI will be assessed for both groups.

The bivariate analysis will be conducted to determine if there is any association between the outcome and the exposure (the covariates). Unadjusted comparisons between groups of covariates and outcomes will be evaluated using appropriate tests: chi-squared test will be used for categorical variables, t-test will be used for continuous variables, and the Kruskal-Wallis test for non-parametric variables; p-values will be generated. The baseline variables considered demographic data, disease duration (years), methotrexate (yes/no), current steroid therapy (yes/no), present smoking (yes/no).

The difference in efficacy between adherent and nonadherent groups by using change from the baseline in BASDAI and BASFI at the last visit will be determined. P-value <0.05 will be considered statistically significant, without multiplicity adjustment for this post-hoc analysis.

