9.8. Limitations of the Research Methods

No missing data that could lead to bias was an identified limitation in this study.

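### The primary 7-year percentage has no definition, denominator or cut-off, and read literally it understates 7-year persistence among 1-year users

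*Combined protocol and SAP*

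**What the plan says.** Section 9.3 gives the primary outcome: it "was the percentage of patients that have 7 year adherence on Enbrel". Section 9.6 describes the calculation: first-year adherence is assessed, "then the 7-year adherence will be assessed and the percentage of patients that achieve 7-year adherence will be calculated". The only adherence rule in the document covers year one: "first-year adherence is defined as patients having at least 7 consecutive visits in one year of Enbrel treatment". The nearest thing to a longer-term definition is in the secondary objective of section 9.1, which contrasts "the adherent group of patients (who continued Enbrel treatment) and the nonadherent group".

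The population is patients who "received etanercept from Baghdad Teaching Hospital (Rheumatology Center) from May 2012 through August 2019" (section 9.1), "with at least 1 year of follow-up after starting their first biologic therapy" (section 9.2) and at least one year on Enbrel (sections 9.2.1 and 9.2.2). Section 9.4 enters everyone who meets the criteria. The tests in section 9.6 are: "chi-squared test will be used for categorical variables, t-test will be used for continuous variables, and the Kruskal-Wallis test for non-parametric variables". None is a time-to-event method. Section 6 puts the end of data collection at 1 October 2020, but no section calls that, or any other date, the follow-up cut-off.

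**The concern.** A patient needs one year of follow-up to enter but seven to succeed. Someone who started in 2016 and never stopped is eligible, yet cannot have reached 7 years by 2019 or 2020. If such patients stay in the denominator as failures, the primary figure reflects when patients started as well as whether they stayed on drug. The error runs towards the hypothesis in section 9.2, which expects few patients to adhere over 7 years.

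If adherent instead means still on drug at the cut-off, a patient with just over one year of treatment counts the same as one with seven, and the percentage mixes follow-up lengths. A reader of the report could not tell which quantity was calculated. The BASDAI and BASFI comparison uses the same undefined groups. That consequence is secondary.

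**Working it through.** The plan states no sample size or expected adherence rate, so there is no figure to reproduce. The check asks what the planned percentage would return for a known true value.

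**Inputs from the documents**
- Receipt window (9.1): 1 May 2012 to 31 August 2019, taking whole months, is 2,678 days or 7.33 years.
- Entry: at least 1 year of use and follow-up (9.2, 9.2.1, 9.2.2).
- Cut-off: not stated. Two candidates are 31 August 2019 (end of the window) and 1 October 2020 (end of data collection, section 6).

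**Assumptions, not in the documents**
- All starts fall on or after 1 May 2012, uniformly unless noted.
- The stopping rate is constant after year 1.
- True 7-year persistence among 1-year users is p = 30%, 50% or 70%.

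**Step 1. Share f of eligible patients with 7 years of possible follow-up**
- August 2019: starts up to 31 August 2012 (122 days) out of starts up to 31 August 2018 (2,313 days). f = 122/2,313 = 5.3%. The narrowest reading of the dates gives 62/2,253 = 2.8%.
- October 2020: starts up to 1 October 2013 (518 days) out of starts up to 31 August 2019 (2,678 days). f = 518/2,678 = 19.3%. Other date readings give 458/2,648 = 17.3% to 518/2,313 = 22.4%.

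**Step 2. Uneven starts.** If a patient's position in the entry period follows Beta(1,b), with early starts favoured, the share becomes 1 − (1 − f)^b. For Beta(2,1), with late starts favoured, it becomes f².

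| Start pattern | August 2019 | October 2020 |
|---|---|---|
| Beta(2,1) | 0.3% | 3.7% |
| Uniform | 5.3% | 19.3% |
| Beta(1,3) | 15% | 48% |
| Beta(1,5) | 24% | 66% |
| Beta(1,10) | 42% | 88% |

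These shares are also the highest percentages the literal calculation could return if nobody ever stopped.

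**Step 3. Literal reading.** Reported percentage = p × f. With uniform starts, p = 30/50/70% is reported as 1.6/2.6/3.7% (August 2019) or 5.8/9.7/13.5% (October 2020).

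**Step 4. Still on drug at the cut-off.** Reported percentage = mean of exp(−λ(F − 1)) over potential follow-up F, with λ = −ln(p)/6. For p = 50%, λ = 0.1155.
- August 2019, F uniform from 1 to 7.33: (1 − 0.481)/(0.1155 × 6.33) = 71%.
- October 2020, F uniform from 1.09 to 8.42: (0.990 − 0.424)/(0.1155 × 7.33) = 67%.
- October 2020 with early starts: Beta(1,5) gives 49.2% and Beta(1,10) gives 46.0%, both below the true 50%. A patient followed beyond 7 years must persist past year 7 to count.

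**Step 5. Denominator limited to patients with 7 years of possible follow-up.** Here f = 1, so the simple percentage returns p. Simulation with p = 50% gave 50.2% to 50.4%.

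**The case against.** The strongest defence is that the sponsor may have meant only patients who could be followed for 7 years. Step 5 shows that the simple percentage would then be valid, so it would be wrong to infer that no reading of the plan estimates 7-year persistence. But no section sets that limit, and section 9.4 points the other way by entering everyone who met the criteria. The sequence in section 9.6 could mean that the denominator is first-year adherers only. That would not help, since that group is not stated to be limited by start date either.

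A reader might also infer that the still-on-drug reading always overstates. Step 4 shows otherwise: the sign depends on start dates, which the documents do not give. Nor is the October 2020 ceiling confined to 17% to 22%. That range varies only the reading of the dates, and early-loaded starts take it to 88%, at which a true 50% would read as about 44%. Section 9.1 says patients received etanercept from May 2012, not that they started then, and earlier starts would raise the ceiling further.

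The low bias is relative to 1-year users. Against all initiators, excluding those who stopped within a year pushes the figure up. With f as in Step 1, that is unlikely to reverse the direction.

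Finally, section 9.8 says "No missing data that could lead to bias was an identified limitation in this study". That concerns missing data. A patient still on drug at the cut-off may have no missing values and yet be incompletely followed, so the sentence neither answers the point nor shows that incomplete follow-up was considered and dismissed.

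**Conclusion.** The concern stands and should be resolved before the primary figure is relied on. The plan does not define 7-year adherence, its denominator, its cut-off or the handling of patients still on drug. Carried out literally, it gives a percentage that is too low among 1-year users whenever some eligible patients lack 7 years of possible follow-up. That direction does not depend on the start pattern or the stopping rate.

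The size does depend on the start pattern. Under uniform starts from May 2012, a true 50% would read as 2.6% or 9.7%, and under strongly early starts with the October 2020 cut-off the bias could be modest. On the still-on-drug reading the figure is too high when most potential follow-up is under 7 years, and can be slightly too low with very early starts and a later cut-off. All sizes are illustrations. The documents do not show that the calculation was chosen to favour the hypothesis.

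**What to change.** **Section 9.3.** State one follow-up cut-off date. Use first-dose, stop and last-visit dates if the registry extract holds them. They are not among the listed variables, and sections 10 and 11 describe anonymised data without retrieval of individual patient data, so availability must be confirmed.

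**Section 9.6.** Adopt one of two estimators:
- restrict the 7-year percentage to patients whose first dose was at least 7 years before the cut-off; or
- estimate 7-year persistence by Kaplan-Meier conditional on one year of use (time at risk from year 1), censoring patients still on drug at the cut-off, with a 95% CI and numbers at risk.

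The restriction must be by start date. Merely dropping patients still on drug with under 7 years of follow-up would turn a true 50% into 6.5% to 8.3% (August 2019) or 22% to 24% (September/October 2020).

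Under either option:
- Count patients who stopped attending without a recorded stop as nonadherent in the main analysis, and show the alternative handling as a sensitivity analysis. State the gap without a visit that counts as having stopped attending.
- Say that the 7-year result measures persistence among 1-year users, unlike the visit-based first-year measure, or extend the visit rule to later years.
- Use the same definition for the BASDAI and BASFI groups, so that patients still on etanercept at the cut-off are not classed as nonadherent.
- Disclose the definition as post hoc, since data collection has ended.

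**Cost.** Wording, up to three dates and a standard analysis. Precision at year 7 will be limited. For an assumed 500 patients, uniform starts and a true 50%, the August 2019 cut-off leaves about 26 patients in the restricted percentage (SE about 10 points), or about 13 at risk for Kaplan-Meier (SE about 4 points). October 2020 leaves about 97 (SE about 5 points) or 48 at risk (SE about 3 points).

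The result also rests on an assumption about patients lost to contact. With a true 50%, if half of stops are unrecorded, Kaplan-Meier that censors those patients gives about 0.5^0.5 = 71%. If 3% a year leave the registry while still on drug, counting them as nonadherent gives about 0.5 × exp(−0.18) = 42%. The main and sensitivity results should be reported together as a range.

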9.2.1. Inclusion Criteria

Patients met all of the following inclusion criteria to be eligible for inclusion in the study:

1. Diagnosed SpA patients.
2. 18 years of age and older.
3. Did not receive previous other biological treatments.
4. Patients have at least 1 year on Enbrel.

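### Section 9.6 tests covariates against a yes/no adherence status that, on two of its three possible readings, depends on when the patient started Enbrel; time to discontinuation with censoring should be analysed instead

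*Combined protocol and SAP*

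**What the plan says.** Section 9.6 sets out the covariate analysis: "The bivariate analysis will be conducted to determine if there is any association between the outcome and the exposure (the covariates"). The method is "Unadjusted comparisons between groups of covariates and outcomes will be evaluated using appropriate tests: chi-squared test will be used for categorical variables", with t-tests for continuous and Kruskal-Wallis tests for non-parametric variables. Only p-values are promised, judged at 0.05. The covariates are demographics, disease duration, methotrexate, steroid therapy and smoking. Start year is not among them.

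The section does not say which adherence status these tests use. Three are available:

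- Section 9.3 makes the primary outcome a 7-year status: it "was the percentage of patients that have 7 year adherence on Enbrel".
- Section 9.1 describes the "adherent group of patients (who continued Enbrel treatment"), which is a status at the end of observation.
- Section 9.6 gives a first-year status: "first-year adherence is defined as patients having at least 7 consecutive visits in one year of Enbrel treatment".

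Treatment ran "from May 2012 through August 2019" (section 9.1). Section 9.2 requires patients "with at least 1 year of follow-up after starting their first biologic therapy", and section 9.2.1 adds "Patients have at least 1 year on Enbrel". Nothing requires seven years of possible follow-up. No section plans censoring, a time-to-event method or adjustment for start year.

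**The concern.** Chi-squared and t-tests on a yes/no status are sound when every patient had the same opportunity to reach that status. Here the opportunity varies from one year to a little over seven. On 7-year status, a patient who started in 2015 and is still on drug at the end counts as nonadherent. On continued versus stopped, the same patient counts as adherent partly because there was less time to stop. The two readings depend on start date in opposite directions, and both discard the time of stopping.

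Two things are at stake. A covariate truly related to stopping may be missed, because the status carries little information about stopping. A covariate unrelated to stopping may be flagged, if its frequency changed over the intake years. In neither case does the plan report an effect size that would let a reader judge the result.

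**Working it through.** The plan states no figure to reproduce: no sample size, stopping rate or power. The check is therefore arithmetic on the calendar, followed by simulation under stated assumptions.

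**Inputs from the documents.** The treatment window is May 2012 through August 2019, at most about 7.33 years (section 9.1). Everyone has at least 1 year on drug (sections 9.2.1 and 9.2.2). Data collection began on 01 September 2020 (section 6). The end of follow-up is not stated, so both August 2019 and September 2020 were tried.

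**Inputs assumed.** n=200; even starts; stopping rate h of 0.1 to 0.2 per year after year 1; a binary covariate; two-sided 0.05.

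**Who can reach seven years.**
- Follow-up to August 2019: starts span 7.33 − 1 = 6.33 years, and only the first 7.33 − 7 = 0.33 years qualify. The share is 0.33/6.33 = 5.2%.
- Follow-up to September 2020: (8.33 − 7)/7.33 = 18.1%.

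**How many would be 7-year adherent.** Given the opportunity, the probability of staying on drug to year 7 is exp(−6h), which is 0.549 for h=0.1 and 0.301 for h=0.2.
- August 2019: 200 × 0.052 × 0.549 = 5.7 patients, or 200 × 0.052 × 0.301 = 3.1.
- September 2020: 200 × 0.181 × 0.549 = 19.9 patients, or 200 × 0.181 × 0.301 = 10.9.

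A chi-squared test with so few patients in one group has little power.

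**How continued-versus-stopped depends on start date.** With follow-up C, the probability of still being on drug is exp(−h(C − 1)). At h=0.1 it is exp(−0.633) = 0.53 for the earliest starter (C = 7.33) and exp(−0.1) = 0.90 for a patient with C = 2. At h=0.2 the pair is 0.28 and 0.82. Drug effect and covariates are identical in these pairs; only the start date differs.

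**Simulation (n=200, ranges over both cut-offs and both stopping rates).**

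| Setting | 7-year status | Continued vs stopped | Log-rank, censored |
|---|---|---|---|
| Covariate doubles stopping: power | 2-23% | 75-83% | 80-95% |
| No effect, prevalence drifts 60% to 40% | 3-11% | 9-11% | about 5% |
| No effect, prevalence drifts 70% to 30% | 6-33% | 16-31% | about 5% |

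The ends of these ranges move by a few percentage points with the covariate's prevalence and with whether 10% is read as a rate or an annual probability. The ordering does not change.

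**Sensitivity.**
- Without drift, no test exceeds about 6%.
- At n=100 with the August 2019 cut-off, 7-year status flags a drifting covariate 1-5% of the time, so there is no inflation.
- With prevalence drifting between 30% and 60% and the August 2019 cut-off, the rates on 7-year status are 3-9% at n=200 and 9-19% at n=500. On continued versus stopped they are 12-20% and 23-39%. Log-rank stays at 3.5-6.5%.
- With front-loaded starts, 37% of patients could reach seven years. Power on 7-year status for a doubled stopping rate then runs from 23% to 100% over n=100 to 1000.

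**The case against.** The strongest reply is that the harm is conditional and the analysis minor. Much of this stands.

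- A reader might infer that real associations will mostly be missed. The documents do not support that in general. On continued versus stopped, power is 75-83% against 80-95% for log-rank, a modest loss. The heavy loss belongs to 7-year status with evenly spread starts, and it shrinks if starts were front-loaded and the sample is large.
- A reader might also infer that methotrexate, steroid use or another covariate will be reported as associated merely because prescribing changed. No section says that any covariate drifted with start year. Even with strong drift at n=200, the false flag appears at most about a third of the time.
- If the tests use first-year adherence, unequal follow-up does not bias them, because every included patient has at least one year.
- If the 7-year analysis were restricted to patients with seven years of possible follow-up, the dependence on start date would go. Under even starts, however, only about 5% of patients (18% with follow-up to September 2020) would remain, and power would stay low.
- Covariate association is not among the objectives in sections 8 and 9.1, and section 9.6 calls the analysis post-hoc and the comparisons unadjusted.

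These points limit the size and importance of the defect. They do not remove it: section 9.6 does not say which status is tested, and two of the three candidates depend on start date with no safeguard.

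**Conclusion.** The point holds in a conditional form. Section 9.6 applies fixed-time tests to a status that partly encodes start date if it means 7-year adherence or continued versus stopped. On 7-year status with even starts, the main consequence is lost power (2-23% against 80-95% for a doubled stopping rate at n=200). On continued versus stopped, it is an inflated false-positive rate when a covariate drifts (9-11% for moderate drift and 16-31% for strong drift, against about 5%). 7-year status can also be inflated under drift, but this depends on the cut-off and the sample size. All these figures rest on assumed sample size, start pattern, stopping rate, drift and end of follow-up, because the documents give none of them. The defect affects a secondary analysis and is worth correcting. It does not by itself affect the primary percentage.

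**What to change.** In section 9.6, state the end of follow-up. Replace the yes/no tests for the adherence outcome with time from Enbrel start to discontinuation, with patients at risk from month 12 (because eligibility requires one year on drug) and censored at last registry contact or data cut-off. Report a Cox hazard ratio with 95% CI for each covariate measured at Enbrel start, and one model adding start year, which also covers the case where stopping itself changed over the intake years. Keep chi-squared and t-tests for describing the groups.

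Before that, clarify whether the methotrexate and steroid values that section 9.3 calls current are the baseline values that section 9.6 assumes. A value recorded after treatment began should not enter the model as a baseline covariate.

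The cost is more than wording. Section 9.3 does not list Enbrel start and stop dates, so these must be extracted from the registry, although any 7-year adherence figure needs them in some form. Proportional hazards must also be checked.

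### The secondary efficacy comparison sets groups formed after baseline side by side with no adjusted analysis planned, and Section 9.8 does not mention confounding

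*Combined protocol and SAP*

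**What the plan says.** Section 9.1 makes the secondary objective a contrast in efficacy between "the adherent group of patients (who continued Enbrel treatment) and the nonadherent group". Section 9.2 states as a hypothesis that "there was no difference between the adherent and the nonadherent group in efficacy". It also says that starting and maintaining treatment followed ACR recommendations.

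The last paragraph of Section 9.6 gives the endpoint, "The difference in efficacy between adherent and nonadherent groups by using change from the baseline in BASDAI and BASFI at the last visit", with significance at p<0.05, a post-hoc label and no multiplicity correction. It does not name a test. The paragraph before it says "Unadjusted comparisons between groups of covariates and outcomes will be evaluated using appropriate tests" and lists the chi-squared test, the t-test and the Kruskal-Wallis test. Section 9.6 also plans to look at baseline and last-visit BASDAI and BASFI by group.

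Section 9.6 contains two adherence measures. One is spelled out: "first-year adherence is defined as patients having at least 7 consecutive visits in one year of Enbrel treatment". The other is not defined: "then the 7-year adherence will be assessed and the percentage of patients that achieve 7-year adherence will be calculated". The efficacy sentence does not say which one forms its groups.

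Section 9.3 lists age, gender, education, smoking, disease duration, MTX and steroid use, and baseline BASDAI and BASFI among the data obtained. Section 9.8 is a single sentence about missing data.

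**The concern.** Whether a patient continues treatment, or attends enough visits, is decided after baseline and not by allocation. Patients who continue may differ from those who stop in disease severity, age, disease duration or co-medication. A plain comparison of change scores then carries those differences, including regression to the mean, together with any effect of adherence. There is also a reverse path: a patient who responds poorly may stop because of it, so that response drives adherence.

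This comparison, at p<0.05, is the one that addresses the hypothesis in Section 9.2. Under the plan, the reader gets one p-value per scale, no adjusted result to set beside it, no statement of the assumption it needs, and no limitation telling the reader to be careful.

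**Working it through.** **Step 1: the text.** The documents state no power, effect size or sample size for this comparison (Section 9.4 says none was set), so there is no figure of the plan to reproduce. Regression, ANCOVA, matching, weighting, propensity methods, confounding and selection bias appear in no section. The covariates in Section 9.6 enter one-at-a-time tests only.

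**Step 2: how far the two analyses can differ.** All inputs here are assumed. Let d be the baseline difference between groups in baseline SDs, r the correlation between baseline and last visit, k the last-visit SD divided by the baseline SD, and b = r × k.

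- If groups would not differ given baseline, the expected last-visit difference is b × d. The change-score difference is then b × d − d = −(1 − b) × d, although adherence has no effect.
- If groups would change in parallel, the expected last-visit difference is d. The adjusted model then shows d − b × d = (1 − b) × d, again with no effect of adherence.

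With r = 0.5 and k = 1, the size is 0.5 × 0.25 = 0.125 SD at d = 0.25, and 0.5 × 0.5 = 0.25 SD at d = 0.5. It is zero at d = 0.

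**Step 3: false rejection rates** (two-sided 5%, noncentral t; p is the share of patients in one group):

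- Change score: nc = (1 − b)d / [√(1 + k² − 2rk) × √(1/n1 + 1/n2)], df = N − 2.
- Adjusted: nc = (1 − b)d / [k√(1 − r²) × √(1/n1 + 1/n2) × √(1 + p(1 − p)d²)], df = N − 3.

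For 50 per group, √(1/50 + 1/50) = 0.2. At d = 0.5:

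- Change score: nc = 0.25 / (1 × 0.2) = 1.25, giving 23.6%.
- Adjusted: nc = 0.25 / (0.866 × 0.2 × 1.031) = 1.40, giving 28.4%.

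| Groups | d | Change score, if no difference given baseline | Adjusted, if parallel change |
|---|---|---|---|
| 50 / 50 | 0 | 5% | 5% |
| 50 / 50 | 0.25 | 9.5% | 10.9% |
| 50 / 50 | 0.5 | 23.6% | 28.4% |
| 20 / 80 | 0.25 | 7.9% | 8.8% |
| 20 / 80 | 0.5 | 16.8% | 20.2% |

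In each column the other analysis stays at 5%. At d = 0.5, with r from 0.3 to 0.7 and k from 0.7 to 1.4, the ranges are 5–47% (change score) and 5–81% (adjusted) for 50/50, and 5–33% and 5–63% for 20/80.

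**Step 4: follow-up time.** Section 9.1 covers treatment "from May 2012 through August 2019": 8 months in 2012, 72 in 2013–2018 and 8 in 2019, or 88 months. Seven years is 84 months, and 88 − 84 = 4. If starts fall inside the window, only patients starting in about the first 4 months can be seen for 84 months. If the last visit also follows Enbrel use, a 7-year split gives times of 84–88 months in the adherent group and 12 to under 84 in the other (Sections 9.2.1 and 9.2.2 require at least 1 year). These times do not overlap, so adjusting for time would be extrapolation. The first-year split implies no such separation. The choice of split therefore decides what the model can estimate.

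**The case against.** The strongest reply is that the plan does not claim adjusted inference. It uses the word unadjusted, calls the work post-hoc, places efficacy second, and plans baseline comparisons that would reveal an imbalance. Change from baseline already subtracts the baseline score, and the figures above do not show the adjusted model to be safer: its range reaches 81% against 47%. All of that is fair. What remains is that seeing an imbalance does not remove it, that subtracting baseline is sound only under parallel change, which the plan never states, and that the post-hoc label is attached to multiplicity and does not disclose confounding. The figures support showing both analyses; they do not support replacing one by the other.

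A reader might infer more than the text allows on two points:

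- **That the plan prescribes an unadjusted test for efficacy.** The efficacy sentence names no test. The unadjusted label and the test list belong to the preceding paragraph on covariates and outcomes. Carrying them over is plausible, but the firm statement is that no adjusted analysis is specified.
- **That patients selected themselves.** Section 9.2 says that maintaining treatment followed recommendations, so continuation was at least partly a guided decision. Groups defined by post-baseline continuation is the accurate description. It makes reverse causation more pressing, and a covariate model does not remove that.

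The unclear group definition is partly a separate gap. It belongs here only because the model cannot be specified without it.

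**Conclusion.** The point holds as a worthwhile, inexpensive improvement to the secondary analysis. The comparison that addresses a stated hypothesis involves groups formed after baseline, has no adjusted analysis beside it, and carries no mention of confounding in Section 9.8. The primary outcome, the percentage with 7-year adherence, is not affected.

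The size of any bias is unknown: the documents give no N, SD, correlation or imbalance. Baseline-score imbalance contributes nothing if the groups are balanced on it. The rejection rates rest wholly on assumed inputs and show only that the choice of analysis can matter. The conclusion rests on the text and not on them.

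It would go too far to conclude that the planned change-score comparison is wrong, or that an adjusted result would be the correct one. Each needs its own assumption, and the documents give no basis for preferring either.

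**What to change.** 1. In Section 9.6, keep the planned change-score difference. For BASDAI and BASFI separately, add a linear model of last-visit score on adherence group, adjusted for that scale's baseline score, age and gender. Label it a sensitivity analysis added after data collection, which ended on 01 October 2020 (Section 6). Add disease duration, smoking, MTX and steroid use where they can be taken as baseline values and there are enough patients. If their timing cannot be confirmed, say so.
2. Report both differences with 95% CIs and the assumption behind each: parallel change for the change score; no difference given baseline and covariates, absent an adherence effect, for the model. Treat neither as right by default.
3. State whether the first-year visit measure or 7-year continuation forms the efficacy groups, and report time to last visit by group.
4. In Section 9.8, list residual confounding, grouping defined after baseline (poor response may lead to stopping, which the model does not remove) and unequal follow-up.

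The cost is one extra model per scale in SPSS, on variables Section 9.3 already lists, and a few sentences. The model would not be pre-specified, and the two results may differ and need interpretation. Covariate dates may be impossible to check, since the data are anonymized (Section 10) and Section 11 says individual data were neither retrieved nor validated. The core model does not depend on that check.
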